## Study timeline for the Primary Study Population

## 9.2.2 Study population

The pre-matched study cohort will consist of patients initiating Olodaterol/Tiotropium Bromide or Umeclidinium/Vilanterol between 17 November 2015 and 31 March 2018.

The following exclusion criteria will then be applied:

Aged <40 years.

Enrolment with medical and pharmacy coverage prior to the cohort entry < 180 days.

Never had COPD diagnosis on the cohort entry date or prior to cohort entry.

A record for dispensed Olodaterol/Tiotropium Bromide delivered with Respimat inhalator or Umeclidinium/Vilanterol delivered with the Ellipta Inhaler during the 180-day baseline prior to cohort entry.

[figure not shown]
Diagnosis of asthma any time prior to cohort entry.

Diagnosis of lung cancer any time prior to cohort entry.

Diagnosis of lung transplant any time prior to cohort entry.

Figure 2

Below depicts the flow diagram of patients.

Diagnosis of COPD (ICD-9: 491.\*, 492.\*, 496.\*; ICD-10: J41.0, J41.1, J41.8, J42.\*, J43.0, J43.1, J43.2, J43.8, J43.9, J44.0, J44.1, J44.9) will be defined as the presence of an inpatient or outpatient claim.

Diagnosis of asthma (ICD-9: 493.\*; ICD-10: J45, J45.20, J45.21, J45.22, J45.90\*, J45.99\*) will be defined as either 1 inpatient claim or 2 outpatient events 30-365 days apart.

Diagnosis of lung cancer (ICD-9: 162.2, 162.3, 162.4, 162.5, 162.8, 162.9, 231.2; ICD-10: C34.00, C34.01, C34.02, C34.10, C34.11, C34.12, C34.2, C34.30, C34.31, C34.32, C34.80, C34.81, C34.82, C34.90, C34.91, C34.92, C7A.090, D02.20, D02.21, D02.22, Z85.118) will be defined as either 1 inpatient claim or 2 outpatient events 30-365 days apart.

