### Matched Cohort

A matched propensity score analysis will be used to assess comparative persistence between the two exposure comparison groups. Logistic regression will be used to calculate the propensity to initiate Olodaterol/Tiotropium Bromide versus Umeclidinium/Vilanterol given all covariates (except components of the Charlson Comorbidity index) listed in [section 9.3.3](#), according to the following model:

$$\text{Logit}(\text{Treatment} | X_1, X_2, \dots, X_n) = \beta_0 + \beta_1 * X_1 + \beta_2 * X_2 + \dots + \beta_n * X_n$$

Any covariates which are collinear with each other will be dropped from the analysis (if it causes failure of model to converge). The propensity score will then be used to identify up to 2 initiators of Umeclidinium/Vilanterol for each initiator of Olodaterol/Tiotropium Bromide with the same propensity score ( $\pm$  a caliper of 5%) as the corresponding initiator of Olodaterol/Tiotropium Bromide (Austin 2011).

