#### 9.7.1.3 Comparative Persistence

- Relative Rate of Discontinuation of Olodaterol/Tiotropium Bromide vs Umeclidinium/Vilanterol in the Unmatched Cohort

Multivariable Cox proportional hazards models with all variables (except components of the Charlson Comorbidity index) in [section 9.3.3.](#) will be used to estimate the hazard ratios (HRs) and 95% CIs for Olodaterol/Tiotropium Bromide compared to patients treated with Umeclidinium/Vilanterol during follow-up for incident discontinuations, according to the following model:

$$h(t | \text{Treatment}, X_1, \dots, X_n) = h(t_0) * \exp(\beta_1 * \text{Treatment} + \beta_2 * X_2 + \dots + \beta_n * X_{n+1})$$

Where treatment can be 1=Stiolto or 0=Anoro and t = time to discontinuation

- Relative Risk of Discontinuation of Olodaterol/Tiotropium Bromide vs Umeclidinium/Vilanterol in the Unmatched Cohort

Multivariable logistic regression will be used to assess relative risk of discontinuation and 95% CIs for Olodaterol/Tiotropium Bromide compared to patients treated with Umeclidinium/Vilanterol during follow-up for incident discontinuations, according to the following model using all covariates (except components of the Charlson Comorbidity index) in [section 9.3.3.](#):

$$\text{Logit}(\text{Discontinuation}=1 | \text{Treatment}, X_1, X_2, \dots, X_n) = \beta_0 + \beta_1 * \text{Treatment} + \beta_2 * X_2 + \dots + \beta_n * X_{n+1}$$

- Relative Rate of Discontinuation of Olodaterol/Tiotropium Bromide vs Umeclidinium/Vilanterol in the Matched Cohort

Cox proportional hazards models with treatment as the only independent variable will be used to estimate the hazard ratios (HRs) and 95% CIs for Olodaterol/Tiotropium Bromide

compared to patients treated with Umeclidinium/Vilanterol during follow-up for incident discontinuations, according to the following model:

$$h(t | \text{Treatment}, X) = h_0(t) * \exp(\beta_1 * \text{Treatment})$$

Where treatment can be 1=Stiolto or 0=Anoro and t = time to discontinuation

- Relative Risk of Discontinuation of Olodaterol/Tiotropium Bromide vs Umeclidinium/Vilanterol in the Matched Cohort

Logistic regression will be used to assess relative risk of discontinuation and 95% CIs for Olodaterol/Tiotropium Bromide compared to patients treated with Umeclidinium/Vilanterol during follow-up for incident discontinuations, according to the following model:

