### 9.7.2 Sensitivity Analysis

Four sensitivity analyses will be conducted. For these analyses, in the interest of reducing the number of additional tables, only the descriptive statistics for the matched population ([Annex Table 2](#)), and primary results ([Annex Tables 4](#) and [5](#)) will be reported.

Two sensitivity analyses will be conducted to evaluate the robustness of the outcome definition:

1. Use of a 30-day Grace Period

Restrict the 60-day allowable grace period used to define the discontinuation outcome to 30 days to allow a gap of one month. This sensitivity analysis may be useful if the 60-day grace period is too lenient, as the usual day's supply of Stiolto is 30 days.

2. Use of a 90-day Grace Period

Since neither the Olodaterol/Tiotropium Bromide or Umeclidinium/Vilanterol drug products are available as generic formulations, the relatively high price of these medications may lead some patients to space out their doses to greater than the recommended dosing schedule or use one puff instead of two to prolong their medication supply. Patients may also neglect to take their medications due to forgetfulness or because they become less symptomatic. Thus, we will also increase the 60-day allowable grace period used to define the discontinuation outcome, to 90 days.

Two sensitivity analyses will be conducted in an attempt to increase the sample size:

3. Start Patient Identification Period in 21 May 2015

The primary identification period starts 180 days after Stiolto Respimat was approved by FDA for use in the US (21 May 2015) on 17 November 2015. This sensitivity cohort will start the patient identification period immediately upon FDA approval on 21 May 2015.

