History of Hospitalization due to Respiratory Condition	1 Inpatient 
Diagnosis Code (Principal), ICD-9 is any of: { "415.1", "415.11", "415.12", "415.13", "415.19", "465", "465.0", "465.8", "465.9", "466", "466.0", "466.1", "466.11", "466.19", "480.0", "480.1", "480.2", "480.3", "480.8", "480.9", "481", "482.0", "482.1", "482.2", "482.30", "482.31", "482.32", "482.39", "482.40", "482.41", "482.42", "483.0", "483.1", "483.8", "484.1", "484.3", "484.5", "484.6", "484.7", "484.8", "486", "487.0", "488.01", "488.11", "488.81", "490", "491", "491.0", "491.1", "491.2", "491.20", "491.21", "491.22", "491.8", "491.9", "492.0", "492.8", "493.0", "493.00", "493.01", "493.02", "493.1", "493.10", "493.11", "493.12", "496", "515", "516.3", "516.30", "516.31", "516.32", "516.8", "516.9", "518.81", "518.83", "518.84" }
 
Diagnosis Code (Principal), ICD-10 is any of: { "A01.03", "A02.22", "A37.01", "A37.11", "A37.81", "A37.91", "A40.3", "A50.04", "A54.84", "B01.2", "B05.2", "B06.81", "B77.81", "B95.3", "B96.0", "B96.1", "I26.9", "I26.90", "I26.92", "I26.99", "J06", "J06.0", "J06.9", "J09.X1", "J09.X2", "J10.0", "J10.00", "J10.01", "J10.08", "J10.1", "J11.0", "J11.00", "J11.08", "J11.1", "J12", "J12.0", "J12.1", "J12.2", "J12.3", "J12.8", "J12.81", "J12.89", "J12.9", "J13", "J14", "J15", "J15.0", "J15.1", "J15.2", "J15.20", "J15.21", "J15.211", "J15.212", "J15.29", "J15.3", "J15.4", "J15.5", "J15.6", "J15.7", "J15.8", "J15.9", "J16", "J16.0", "J16.8", "J17", "J18", "J18.0", "J18.1", "J18.2", "J18.8", "J18.9", "J20", "J20.0", "J20.1", "J20.2", "J20.3", "J20.4", "J20.5", "J20.6", "J20.7", "J20.8", "J20.9", "J21.0", "J22", "J39", "J39.3", "J39.8", "J39.9", "J40", "J41", "J41.0", "J41.1", "J41.8", "J42", "J43", "J43.0", "J43.1", "J43.2", "J43.8", "J43.9", "J44.0", "J45", "J45.2", "J45.20", "J45.21", "J45.22", "J45.3", "J45.30", "J45.31", "J45.32", "J45.4", "J45.40", "J45.41", "J45.42", "J45.5", "J45.50", "J45.51", "J45.52", "J45.9", "J45.90", "J45.901", "J45.902", "J45.909", "J45.99", "J45.991", "J45.998", "J47.0", "J68.0", "J84.111", "J84.116", "J84.117", "J84.2", }

	“J85.1”, “J96”, “J96.9”, “J96.90”, “J96.91”, “J96.92”, “J96.0”, “J96.00”, “J96.01”, “J96.02”, “J96.1”, “J96.10”, “J96.11”, “J96.12”, “J96.2”, “J96.20”, “J96.21”, “J96.22”, “J98”, “J98.2”, “J98.3”, “J98.8” }

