History of Hospitalization due to Respiratory Condition; n (%)			
Acute Myocardial Infarction; n (%)			
Angina Pectoris; n (%)			
Peripheral Vascular Disease; n (%)			

	Tio/Olo	Umech/Vi	Standardized Difference (95% CI)
Heart Failure; n (%)			
Hypertension; n (%)			
Upper Respiratory Tract Infection; n (%)			
Lower Respiratory Tract Infection; n (%)			
Cardiac Arrhythmias; n (%)			
Cerebrovascular Disease; n (%)			
All Cancers (except non-melanoma skin cancer); n (%)			
Allergic Rhinitis; n (%)			
Chronic Sinusitis; n (%)			
Bronchiectasis; n (%)			
Pneumonia; n (%)			
Chronic Bronchitis; n (%)			
Exertional Breathlessness; n (%)			
Anxiety; n (%)			
Dementia; n (%)			
Depression; n (%)			
Osteoporosis; n (%)			
Charlson-Deyo Comorbidity Index, continuous			
mean (sd)			
median [IQR]			
Charlson-Deyo Comorbidity Index, categorical			
0; n (%)			
1; n (%)			
2; n (%)			
3+; n (%)			
Acute Liver Injury or Failure; n (%)			
Chronic Kidney Disease (without ESRD); n (%)			
End Stage Renal Disease; n (%)			
Rheumatologic Disease; n (%)			

	Tio/Olo	Umecl/Vi	Standardized Difference (95% CI)
Peptic Ulcer Disease; n (%)			
Gastroesophageal reflux disease (GERD); n (%)			
Type 1 Diabetes Mellitus; n (%)			
Type 2 Diabetes Mellitus; n (%)			
Type 1 or Type 2 Diabetes with no chronic complications; n (%)			
Type 1 or Type 2 Diabetes with chronic complications; n (%)			
Mild Liver Disease; n (%)			
Moderate to Severe Liver Disease; n (%)			
Renal Disease; n (%)			
Metastatic Solid Tumor; n (%)			
HIV/AIDS; n (%)			
Hemiplegia or Paraplegia; n (%)			
Lifestyle			
Smoking Related Claim or Intervention; n (%)			
Vaccination for Influenza; n (%)			
Vaccination for Pneumococcus; n (%)			
Respiratory Function Procedures/Tests			
Pulmonary function tests; n (%)			
Six-minute walk test; n (%)			
Chest X-ray; n (%)			
Chest HRCT; n (%)			

*Tio/Olo, tiotropium/olodaterol; Umecl/Vi, umeclidinium, vilanterol.*

**Table 3.** Absolute Standardized Differences as Measured in the Unmatched vs. Matched Cohorts

	Abs. Std. Diff. (Unmatched)	Abs. Std. Diff. (Matched)	Change	Change (%)
Demographics				
Age on index date				
Gender				
Region				
Insurance Type				
Year of Cohort Entry				
Oral Corticosteroids; n (%)				
Short acting muscarinic antagonist (SAMA), n (%)				
Short acting beta agonist (SABA), n (%)				
Long acting muscarinic antagonist (LAMA), n (%)				
Long acting beta agonist (LABA), n (%)				

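### The ICD-10 list for the respiratory-hospitalization covariate omits J44.1 and J44.9, two of the protocol's own COPD codes

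*Combined protocol and SAP*

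**What the plan says.** Section 9.2.2 gives the protocol's definition of COPD. The ICD-10 list ends "J43.8, J43.9, J44.0, J44.1, J44.9) will be defined as the presence of an inpatient or outpatient claim". The ICD-9 definition is the three families 491, 492 and 496, each with a wildcard.

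Annex 4 defines the respiratory-hospitalization covariate as one inpatient event whose principal diagnosis is on a closed list. The ICD-10 list runs "J43.8', 'J43.9', 'J44.0', 'J45', 'J45.2', 'J45.20", going from J44.0 straight to J45. The ICD-9 list includes "491.2', '491.20', '491.21', '491.22', '491.8', '491.9', '492.0', '492.8" and "493.12', '496', '515".

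The covariate is listed in section 9.3.3 and is not a Charlson component. It therefore enters the propensity score, which is estimated "given all covariates (except components of the Charlson Comorbidity index) listed in" that section (section 9.2.2, Matched Cohort). It also enters the adjusted analyses of the unmatched cohort, described in section 9.7.1.3 as "Multivariable Cox proportional hazards models with all variables (except components of the Charlson Comorbidity index) in" section 9.3.3, with a matching logistic model.

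**The concern.** In a COPD cohort, the covariate meant to identify admissions for respiratory disease leaves out two codes that the protocol itself calls COPD. A patient whose only baseline admission carries J44.1 or J44.9 as principal diagnosis has all-cause hospitalization = yes and respiratory hospitalization = no. On those two variables, that patient looks the same as one admitted for a non-respiratory reason.

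Respiratory admission is in the model because section 9.12 treats the listed covariates as presumed confounders. If the flag misses part of what it is named for, matching and adjustment on it are less complete than they appear. The planned diagnostics would not show this. Tables 2 and 3 of Annex 5 assess balance on the same flag ("History of Hospitalization due to Respiratory Condition; n" and percent), so good balance there says nothing about the missed admissions. The sensitivity analyses in section 9.7.2 vary the grace period ("Two sensitivity analyses will be conducted to evaluate the robustness of the outcome definition"), the start date and the asthma exclusion. None varies a covariate code list.

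**Working it through.** **1. ICD-10 codes side by side.** Inputs: the COPD definition in section 9.2.2 and the ICD-10 list for the covariate in Annex 4.

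| Section 9.2.2 COPD entry | In the Annex 4 list? |
|---|---|
| J41.0, J41.1, J41.8 | yes (3) |
| J42 | yes (1) |
| J43.0, J43.1, J43.2, J43.8, J43.9 | yes (5) |
| J44.0 | yes (1) |
| J44.1 | **no** |
| J44.9 | **no** |

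Present: 3 + 1 + 5 + 1 = 10 of 12. Missing: 2 of 12.

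**2. Does the matching rule matter?** Under exact matching J44.1 and J44.9 are missed. Under prefix matching they are still missed, because J44 itself is not listed and J44.0 does not cover them. No wildcard is attached, although Annex 4 writes an asterisk where it wants a family (R06.0* for exertional breathlessness, O98.7* for HIV/AIDS). The run J43.9, J44.0, J45 is unbroken, so a damaged table does not explain the gap.

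**3. ICD-9 half of the same measure.** It lists 491 and its subcodes, 492.0 and 492.8, and 496, so all three families of section 9.2.2 are covered. The two halves of one covariate treat COPD admissions differently.

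**4. What the flag is for.** Section 9.3.3 lists 5 demographic + 21 medication + 34 comorbidity/symptom + 3 lifestyle + 4 test covariates = 67. Only this one is built to separate respiratory from other admissions.

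**5. How much of the baseline is ICD-10?** The documents give no date for the change from ICD-9 to ICD-10, so this step rests on an assumed date: 1 October 2015, varied from 1 July 2015 to 1 January 2016.

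- Entry window (section 9.2.2): 17 November 2015 to 31 March 2018, both included = 866 days.
- Baseline (section 9.2.1): the 180 days ending the day before entry. It is fully ICD-10 when entry date − 180 days is on or after the switch.
- For 1 October 2015, the first such entry date is 29 March 2016, which is 133 days after the window opens: 866 − 133 = 733 days, and 733/866 = 84.6%.
- Mean ICD-10 share: the first 133 entry days carry 133, 132, …, 1 ICD-9 days, which sum to 133 × 134/2 = 8,911. So 1 − 8,911/(866 × 180) = 94.3%.

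| Assumed switch | Fully ICD-10 | Mixed | Fully ICD-9 | Mean ICD-10 share of baseline |
|---|---|---|---|---|
| 1 Jul 2015 | 825 (95.3%) | 41 | 0 | 99.4% |
| 1 Oct 2015 | 733 (84.6%) | 133 | 0 | 94.3% |
| 1 Jan 2016 | 641 (74.0%) | 179 | 46 (5.3%) | 84.4% |

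These are shares of calendar days, not of patients. They show only that the primary analysis relies mainly on the half of the definition with the gap.

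**6. A separate point, on eligibility.** The ICD-10 asthma exclusion in section 9.2.2 lists bare J45, J45.20 to J45.22, J45.90* and J45.99*. Because it marks wildcards elsewhere in the same list, a literal reading of J45 omits J45.3x to J45.5x (12 entries that Annex 4 does list for the hospitalization covariate). The ICD-9 side uses 493 with a wildcard. If J45 is meant as a parent code, nothing is omitted.

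**The case against.** The omission is plain from the text; the serious objection is to its importance.

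- **No consequence is shown.** Two of 12 counts codes, not admissions. Both arms use the same list. The primary matched Cox model has treatment as its only term, so the flag reaches the primary hazard ratio only as one input to the propensity score. The multivariable models are secondary. This stands, and it limits the claim.
- **Other covariates recover information.** All-cause hospitalization counts every inpatient event. Pneumonia, lower respiratory infection, bronchiectasis and chronic bronchitis are each set by one inpatient code in any position, so an admission with J44.1 as principal diagnosis and one of those codes as secondary still leaves a trace. The Charlson index scores a COPD event, and oral corticosteroids, antibiotics, oxygen and emergency visits are in the model. This also stands in part. However, the printed ICD-10 lists for those four diagnosis flags contain no J44 code, and the Charlson item does not separate admissions from other claims.
- **The list has other gaps.** The ICD-9 half has only 493.0x and 493.1x for asthma and lacks 482.49, 482.8x, 482.9, 485 and 494. The ICD-10 half lacks J47.1, J47.9 and J21.8. Other measures in Annex 4 or the asthma definition in section 9.2.2 use these codes. So the contrast between a complete ICD-9 half and an incomplete ICD-10 half holds for COPD codes only. That does not remove the COPD gap.
- **The plan has a correction route.** Section 9.12 provides for medical review of code lists before implementation. Section 9.8 provides for a second-analyst check and for changes by amendment. These may catch the gap, but the list as written remains wrong until it is edited.
- **The asthma point** depends on an unstated matching rule, and sensitivity analysis 4 drops the asthma exclusion, so it is partly covered. It is not needed for the main conclusion.

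**Conclusion.** The concern holds. The list omits 2 of the protocol's 12 ICD-10 COPD entries under either matching rule, while the ICD-9 half omits none of the three COPD families. Nothing in the documents gives a reason for the difference.

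The precise scope is this: an admission is missed when J44.1 or J44.9 is its principal diagnosis. The patient is then misclassified unless another baseline admission carries a listed principal code. An admission with, for example, J96.0 or J18.9 as principal diagnosis is still counted.

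The omission itself needs no assumption. The statement that most of the baseline falls under ICD-10 rests on the assumed switch date. The number of misclassified patients, and the size and direction of any bias in the hazard ratio, cannot be derived from the documents. With the same list in both arms and partial recovery through other covariates, the effect may be small, but the planned balance tables and sensitivity analyses cannot establish that. This is a definite error in a covariate definition that should be corrected; it does not by itself invalidate the comparison. Confidence is high for the J44 omission and moderate for the asthma point.

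**What to change.** 1. Add J44.1 and J44.9 to the ICD-10 list of the covariate in Annex 4. Coverage of the protocol's own COPD codes rises from 10 of 12 to 12 of 12.
2. State in Annex 4 whether codes match exactly or as prefixes. While the list is open, check it against the other respiratory lists in Annex 4 for the further gaps named above.
3. Rerun the propensity model, matching, balance tables and outcome models, and the four sensitivity analyses. Analyses 3 and 4 use different cohorts, so they need their own propensity scores and matching.
4. Record the change as an amendment, as section 9.8 requires.
5. Separately, reconcile the ICD-10 asthma exclusion in section 9.2.2 with its ICD-9 side, for example by writing J45.*.

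Cost: for the COPD correction, a two-code edit and one rerun of the programmed analyses. The flag is not an eligibility criterion, so the pre-matched counts of 14,751 (3,889 and 10,862) do not change; the matched sets may. The asthma edit needs a rerun of the attrition table, and the counts need restating only if that table changes.

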Heart Failure	
1 Inpatient
 
Diagnosis Code (Any Position), ICD-9 is any of: { “428”, “428.0”, “428.1”, “428.2”, “428.20”, “428.21”, “428.22”, “428.23”, “428.3”, “428.30”, “428.31”, “428.32”, “428.33”, “428.4”, “428.40”, “428.41”, “428.42”, “428.43”, “428.9” }
 
Diagnosis Code (Any Position), ICD-10 is any of: { “I50”, “I50.9”, “I50.2”, “I50.20”, “I50.21”, “I50.22”, “I50.23”, “I50.3”, “I50.30”, “I50.31”, “I50.32”, “I50.33”, “I50.4”, “I50.40”, “I50.41”, “I50.42”, “I50.43” }

Hypertension	
1 Inpatient or 2 Outpatient (30 – 365 days apart)
 
Diagnosis Code (Any Position), ICD-9 is any of: { “401”, “401.0”, “401.1”, “401.9”, “402”, “402.0”, “402.00”, “402.1”, “402.10”, “402.9”, “402.90”, “403”, “403.0”, “403.00”, “403.01”, “403.1”, “403.10”, “403.11”, “403.9”, “403.90”, “403.91”, “404”, “404.0”, “404.00”, “404.01”, “404.02”, “404.03”, “404.1”, “404.10”, “404.11”, “404.12”, “404.13”, “404.9”, “404.90”, “404.91”, “404.92”, “404.93”, “405”, “405.0”, “405.01”, “405.09”, “405.1”, “405.11”, “405.19”, “405.9”, “405.91”, “405.99” }
 
Diagnosis Code (Any Position), ICD-10 is any of: { “I10”, “I11.9”, “I12.0”, “I12.9”, “I13.0”, “I13.10”, “I13.11”, “I13.2”, “I15.0”, “I15.8” }

Upper Respiratory Infection (with no sinusitis)	
1 Inpatient or 2 Outpatient (30 – 365 days apart)
 
Diagnosis Code (Any Position), ICD-9 is any of: { “034”, “034.0”, “034.1”, “460”, “461”, “461.0”, “461.1”, “461.2”, “461.3”, “461.8”, “461.9”, “462”, “463”, “464”, “464.0”, “464.00”, “464.01”, “464.1”, “464.10”, “464.11”, “464.2”, “464.20”, “464.21”, “464.3”, “464.30”, “464.31”, “464.4”, “464.5”, “464.50”, “464.51”, “465”, “465.0”, “465.8”, “465.9”, “487”, “487.1”, “487.8” }
 
Diagnosis Code (Any Position), ICD-10 is any of: { “J03.00”, “J03.01”, “A38”, “A38.8”, “A38.9”, “J00”, “J01”, “J01.9”, “J01.90”, “J01.8”, “J01.80”, “J01.0”, “J01.00”, “J01.01”, “J32.0”, “J01.1”, “J01.10”, “J01.11”, “J32.1”, “J01.2”, “J01.20”, “J01.21”, “J32.2”, “J01.3”, “J01.30”, “J01.31”, “J32.3”, “J02”, “J02.8”, “J02.9”, “J04”, “J04.0”, “J05”, “J05.0”, “J04.1”, “J04.10”, “J04.11”, “J04.2”, “J05.1”, “J05.10”, “J05.11”, “J04.3”, “J04.30”, “J04.31”, “J06”, “J06.9”, “J11.89”, “J11.8”, “J11.1”, “J11”, “J10.89”, “J10.8”, “J10.1”, “J10.00”, “J10.0”, “J10”, “J09.X2”, “J09.X9”, }

	“J09.X”, “J09” }

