Pneumonia	
1 Inpatient or 2 Outpatient (30 – 365 days apart)
 
Diagnosis Code (Any Position), ICD-9 is any of: { “003.22”, “020.3”, “020.4”, “020.5”, “021.2”, “022.1”, “031.0”, “039.1”, “052.1”, “055.1”, “073.0”, “083.0”, “112.4”, “114.0”, “114.4”, “114.5”, “115.05”, “115.15”, “115.95”, “130.4”, “136.3”, “480.0”, “480.1”, “480.2”, “480.3”, “480.8”, “480.9”, “481”, “482”, “482.0”, “482.1”, “482.2”, “482.3”, “482.30”, “482.31”, “482.32”, “482.39”, “482.4”, “482.40”, “482.41”, “482.42”, “482.49”, “482.8”, “482.81”, “482.82”, “482.83”, “482.84”, “482.89”, “482.9”, “483”, “483.0”, “483.1”, “483.8”, “484”, “484.1”, “484.3”, “484.5”, “484.6”, “484.7”, “484.8”, “485”, “486”, “487”, “487.0”, “487.1”, “487.8”, “517.1” }
 
Diagnosis Code (Any Position), ICD-10 is any of: { “A01.03”, “A02.22”, “A20.2”, “A21.2”, “A22.1”, “A31.0”, “A37.01”, “A37.11”, “A37.91”, “A43.0”, “A49.2”, “B01.2”, “B05.2”, “B06.81”, “B25.0”, “B37.1”, “B38.0”, “B38.1”, “B38.2”, “B39.0”, “B39.1”, “B39.2”, “B44.0”, “B58.3”, “B59”, “B77.81”, “J09”, “J09.X”, “J09.X1”, “J09.X2”, “J09.X9”, “J10”, “J10.0”, “J10.00”, “J10.01”, “J10.08”, “J10.1”, “J10.8”, “J10.89”, “J11”, “J11.0”, “J11.00”, “J11.08”, “J11.8”, “J11.89”, “J12.0”, “J12.1”, “J12.2”, “J12.3”, “J12.81”, “J12.89”, “J12.9”, “J13”, “J14”, “J15.0”, “J15.1”, “J15.20”, “J15.211”, “J15.212”, “J15.29”, “J15.3”, “J15.4”, “J15.5”, “J15.6”, “J15.7”, “J15.8”, “J15.9”, “J16.0”, “J16.8”, “J17”, “J18.0”, “J18.1”, “J18.8”, “J18.9” }

Chronic Bronchitis	
1 Inpatient or 2 Outpatient (30 – 365 days apart)
 
Diagnosis Code (Any Position), ICD-9 is any of: { “491”, “491.0”, “491.1”, “491.2”, “491.20”, “491.21”, “491.22”, “491.8”, “491.9” }
 
Diagnosis Code (Any Position), ICD-10 is any of: { “J41”, “J41.0”, “J41.1”, “J41.8”, “J42” }

Exertional Breathlessness	
1 Inpatient or 2 Outpatient (30 – 365 days apart)
 
Diagnosis Code (Any Position), ICD-10 is any of: { “R06.0*” }
 
Diagnosis Code (Any Position), ICD-9 is any of: { “786.0” }

Anxiety	
1 Inpatient or 2 Outpatient (30 – 365 days apart)
 
Diagnosis Code (Any Position), ICD-9 is any of: { “293.84”, “300.0”, “300.00”, “300.02”, “300.09”, “309.21”, “309.24”, “309.28”, “313.0” }
 
Diagnosis Code (Any Position), ICD-10 is any of: { “F06.4”, “F41.1”, “F41.8”, “F41.9”, “F43.22”, “F43.23”, “F93.0”, “F93.8”, “F40”, “F40.8”, “F40.9”, “F41”, “F41.0”, “F41.3” }

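### The Annex 4 Hypertension list omits I11.0 (and ICD-9 402.01, 402.11, 402.91) but includes the parallel heart-and-kidney codes, so some hypertensive patients can be recorded as not hypertensive

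*Combined protocol and SAP*

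**What the plan says.** The Hypertension row of Annex 4 requires one inpatient or two outpatient claims (30 to 365 days apart) with a listed code in any position. Its ICD-10 list is "I10”, “I11.9”, “I12.0”, “I12.9”, “I13.0”, “I13.10”, “I13.11”, “I13.2”, “I15.0”, “I15.8". Its ICD-9 list covers category 402 with "402”, “402.0”, “402.00”, “402.1”, “402.10”, “402.9”, “402.90”, “403", the last entry being the start of the next category. It covers category 404 with "404.00”, “404.01”, “404.02”, “404.03”, “404.1”, “404.10”, “404.11”, “404.12”, “404.13”, “404.9”, “404.90”, “404.91”, “404.92”, “404.93".

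The Heart Failure row just above requires one inpatient claim. It lists only 428.x in ICD-9 and, in ICD-10, "I50”, “I50.9”, “I50.2”, “I50.20”, “I50.21”, “I50.22”, “I50.23”, “I50.3”, “I50.30”, “I50.31”, “I50.32”, “I50.33”, “I50.4”, “I50.40”, “I50.41”, “I50.42”, “I50.43".

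Hypertension is a covariate in section 9.3.3, assessed over the 180 days up to the index date. Section 9.2.2 (Matched Cohort) builds the propensity score "given all covariates (except components of the Charlson Comorbidity index) listed in" section 9.3.3, and section 9.7.1.3 applies the same rule to the multivariable Cox and logistic models. Hypertension is not among the components of the Charlson-Deyo index in Annex 4, so it stays in all of these models under its own name. It is also a line in Tables 2 and 3 of Annex 5.

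**The concern.** The list treats parallel codes differently. In the standard classification (the annex prints no labels), I11.0 and 402.x1 are hypertensive heart disease with heart failure, and I11.9 and 402.x0 are the same disease without it. I13.0, I13.2, 404.x1 and 404.x3 add kidney disease to the form with heart failure. Annex 4 counts a patient as hypertensive when heart failure comes with kidney disease, but not when it comes without. The omitted codes have not been moved to the Heart Failure row either.

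Section 9.12 describes the covariates as hypothesised confounders and undertakes to minimise their misclassification. If the flag is wrong for some patients, matching balances the flag rather than the condition, and Table 3 reports the balance of the flag. The patients at risk of being missed have cardiac involvement, so they are unlikely to be a random subset of hypertensive patients.

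**Working it through.** The plan has no figure to reproduce here. The check is whether each code is in the list, under the two ways a program could read it. The inputs are the 47 ICD-9 and 10 ICD-10 codes of the Hypertension row and the codes of the Heart Failure row.

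| Code | Hypertension, exact match | Hypertension, prefix match | Heart Failure list |
|---|---|---|---|
| I11.9 | yes | yes | no |
| **I11.0** | **no** | **no** | no |
| 402.00, 402.10, 402.90 | yes | yes | no |
| **402.01, 402.11, 402.91** | **no** | yes | no |
| I13.0, I13.2 | yes | yes | no |
| 404.01, 404.03, 404.11, 404.13, 404.91, 404.93 | yes | yes | no |

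1. *I11.0.* It is missed under both readings, because the list has no I11 parent for it to fall under.

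2. *The 402.x1 codes.* Under prefix matching the parents 402, 402.0, 402.1 and 402.9 would catch them. Under exact matching they are lost. The annex points to exact matching in two ways. It adds an asterisk where it means a code family: the Exertional Breathlessness row reads "is any of: { “R06.0" followed by one, and the HIV/AIDS row has O98.7 with one. The Hypertension row has none. It also lists parents and children together (402.0 and 402.00), which prefix matching would make redundant.

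3. *Whether the omission looks deliberate.* A rule keeping heart-failure codes out of Hypertension would also have removed I13.0, I13.2, 404.x1 and 404.x3, and all of these are present. Block 403 carries its .x1 codes and block 404 its .x1 to .x3 codes. Only block 402 stops at .x0.

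4. *Secondary hypertension.* The ICD-9 list carries block 405 in full (405; 405.0, .01, .09; 405.1, .11, .19; 405.9, .91, .99). The ICD-10 list has only I15.0 and I15.8, so I15.1, I15.2 and I15.9 are missing. No I15 parent is listed, so this also holds under both readings.

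5. *Who is affected.* A patient is misrecorded only if the listed codes do not by themselves meet the one-inpatient or two-outpatient rule in the baseline window, and would meet it once the omitted codes counted. Adding codes can only move patients from no to yes. The hypertension prevalence in Table 2 is therefore understated or unchanged, never overstated.

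6. *How many.* This would need the frequency of I11.0 and 402.x1, the share of those patients without another qualifying code, and the share meeting the claim-count rule. The documents give none of these for the 14,751 new users in section 9.5.

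**The case against.** The strongest case on the other side is that the point is too small to matter. Hypertension is one binary flag among many covariates. Antihypertensives is a separate covariate whose definition in Annex 3 spans ACE inhibitors, angiotensin receptor blockers, beta-blockers, calcium channel blockers and diuretics. Nothing in the documents suggests that I11.0 is used more in one exposure group than in the other. The 402.x1 gap disappears under prefix matching. Section 9.12 promises medical review of code lists before implementation, and section 9.8 allows definitions to be modified.

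Most of this stands and limits the point. The partial proxy and the lack of any evidence of differential coding mean that no bias in the hazard ratio has been shown. The ICD-9 part does depend on the matching rule. What does not stand is the appeal to later review: the list as written is incomplete, and I11.0 is missed under either reading.

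A reader might infer two stronger things:

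- *That every patient with I11.0 is counted as non-hypertensive.* The row does not say that. Anyone whose claims with I10 or another listed code meet the rule is still captured. How often the combination code appears alone depends on coding practice that the documents do not describe.
- *That the Heart Failure row should be extended to the combination codes, or that its lack of I50.1 is an equal fault.* Heart Failure is a Charlson component. It reaches the models only as a point in the index, so extending it would change the Charlson score, which is itself a covariate. Because the row requires an inpatient claim, outpatient I11.0 claims would still not set it. I50.1 would be caught by the listed parent I50 under prefix matching. Any change to Heart Failure is a separate choice.

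**Conclusion.** The Hypertension list is internally inconsistent and should be corrected. For I11.0 and the I15 codes this rests on the lists alone. For 402.01, 402.11 and 402.91 it also assumes exact matching, which the annex's notation supports but does not state. Patients whose only qualifying code is one of these are recorded as not hypertensive in the propensity score, the multivariable models and Tables 2 and 3.

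The point is minor. A reader might want to put a share of the cohort on it, but every input to such a figure would be assumed, and the claim-count rule would lower it by an unknown amount. The documents support the direction for the tabulated prevalence, not a size. The effect on the hazard ratio is probably small given the Antihypertensives covariate; that is a judgement, not a calculation.

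**What to change.** In the Hypertension row of Annex 4, add I11.0 to the ICD-10 list and 402.01, 402.11 and 402.91 to the ICD-9 list. Complete I15 (I15.1, I15.2, I15.9) so that it matches the full 405 block. If any of these codes was left out on purpose, say so and give the reason. One sentence in Annex 4 stating that codes without an asterisk are matched exactly would settle the remaining ambiguity. Leave the Heart Failure row as it is for this purpose.

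The cost is an edit to one row, documented as section 9.8 requires, and a rerun of the Hypertension measure before the propensity score is fitted. No new data are needed, and the Charlson score does not change.
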